5.3.1 IND Sponsor Reporting to the FDA

It is the responsibility of the IND Sponsor to make the determination of which SAEs are “serious and unexpected suspected adverse reactions” (SUSARs) as defined in 21 CFR 312.32.

- *Suspected adverse reaction* means any AE for which there is a reasonable possibility that the drug caused the AE.
- *Unexpected adverse event* means an AE that is not listed in the IB or is not listed at the specificity or severity that has been observed.

All SUSARs, as determined by the IND Sponsor, will be reported to the FDA as IND Safety Reports. All IND Safety Reports will be provided to the site PI by the IND Sponsor or delegated representative.

The IND Sponsor will submit an IND Annual Report of the progress of the investigation to the FDA as defined in 21 CFR 312.33.

5.4 Reporting to the Institutional Review Board

The site should follow the reporting procedures and requirements established by the site IRB. The definitions below are provided as guidance and should not supersede the site’s IRB policies. The FDA “Guidance for Clinical Investigators, Sponsors, and IRBs: Adverse Event Reporting to IRBs – Improving Human Subject Protection” is recommended for use and can be found at the following location:

<https://www.fda.gov/downloads/regulatoryinformation/guidances/ucm126572.pdf>.

5.4.1 Unanticipated Problems

An unanticipated problem (UP) is defined as any incident, experience, or outcome that meets all three of the following criteria:

- unexpected in nature, severity, or frequency in relation to the research risks that are described in the protocol, informed consent, IB, other study documents or in consideration of the characteristics of the subject population being studied; **and**
- related to participation in the research; **and**
- suggests that the research places subjects or others at a greater risk of harm (including physical, psychological, economic, or social harm) than was previously known or recognized.

Serious UP: An UP that meets the definition of a SAE or compromises the safety, welfare or rights of subjects or others.

An UP that is not an AE (UPnonAE) is an unanticipated problem that does not fit the definition of an AE, but which may, in the opinion of the investigator, involve risk to the subject, affect others in the research study, or significantly impact the integrity of research data. Such events may also be considered a UP. For example, we will report occurrences of breaches of confidentiality, accidental destruction of study records, or unaccounted-for study drug.

5.4.2 Protocol Deviations

A protocol deviation is defined as any change, divergence, or departure from the IRB-approved study procedures in a research protocol. Protocol deviations are designated as serious or non-serious and further characterized as:

- Those that occur because a member of the research team deviates from the protocol.
- Those that are identified before they occur, but cannot be prevented.
- Those that are discovered after they occur.

Serious Protocol Deviation: A deviation that meets the definition of a SAE or compromises the safety, integrity of the data, welfare or rights of subjects or others.

5.4.3 Non-Compliance

Non-compliance is the failure to comply with applicable NIH Human Research Protections Program (HRPP) policies, IRB requirements, or regulatory requirements for the protection of human subjects. Non-compliance is further characterized as serious, continuing or minor.

“Serious non-compliance” is defined as non-compliance that

- Increases risks, or causes harm, to participants
- Decreases potential benefits to participants
- Compromises the integrity of the NIH-HRPP
- Invalidates the study data

“Continuing non-compliance” is non-compliance that is recurring.

“Minor non-compliance” is non-compliance that is neither serious nor continuing.

5.4.4 Expedited and Annual Reporting to the site IRB

Expedited and annual reporting to the site IRB will be completed by the site per the institutional requirements.

6 STATISTICAL CONSIDERATIONS

6.1 Overview

This study is a Phase I, randomized, open-label, dose-escalation study to examine the dose, safety, tolerability, and immunogenicity of VRC-WEVLP073-00-VP (WEVEE) alone or with alum adjuvant at Day 0 and Week 8. The primary objective relates to safety and tolerability; the secondary and exploratory objectives relate to the immunogenicity of the study product.

6.2 Endpoints

6.2.1 Primary Endpoints: Safety

Assessment of product safety will include clinical observation and monitoring of hematological and chemical parameters. Reactogenicity will be closely monitored for 7 days after each product administration and safety evaluated by clinical visits through the study duration of 36 weeks.

The following parameters will be assessed for all study groups:

- Local reactogenicity signs and symptoms for 7 days after each injection
- Systemic reactogenicity signs and symptoms for 7 days after each injection
- Laboratory measures of safety
- AEs
- SAEs
- New chronic medical conditions

6.2.2 Secondary Endpoints: Immunogenicity

The immunogenicity endpoints are antigen-specific antibody responses as evaluated by virus-specific neutralization assays. The primary time point for immunogenicity evaluation is 4 weeks after the second vaccination.

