1.6 Assessment of Immunogenicity

In this protocol, specimens to evaluate immunogenicity will be taken at baseline and at specified time points. The primary immunogenicity timepoint is 4 weeks after the second vaccination. Measurements of WEVEE-specific humoral immune responses will be assessed by neutralization antibody assays. ELISA and other exploratory assays to assess humoral immune responses may be performed with stored samples. Research samples for immunogenicity assays will be processed at the site and sent directly to the contracted testing laboratory, Battelle, in Columbus, OH. Exploratory immunogenicity assays may also be performed by VRC or contract laboratories, or by other research collaborators.

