3.2 Secondary Objectives

- To evaluate the humoral immunogenicity of VRC-WEVVLP073-00-VP without adjuvant at 4 weeks after the last product administration by virus-specific neutralization assays.
- To evaluate the humoral immunogenicity of VRC-WEVVLP073-00-VP with adjuvant at 4 weeks after the last product administration by virus-specific neutralization assays.

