4.2.5 Study Schedule

The Schedule of Evaluations in Appendix III provides details on the study schedule and the permitted visit windows. A clinician should discuss the target dates and timing of the study vaccination(s) and sample collections before completing a randomization to help ensure that the subject can comply with the projected schedule.

The schedule of study visits, permitted windows for completing the visits, and evaluations performed at each visit are shown in Appendix III. After randomization, deviations from the visit windows in completing study visits and study product administrations are discouraged and will be recorded as protocol deviations, but are permitted at the discretion of the IND Sponsor.

Important Information about Shifting Study Visits

Study visits are scheduled a specific number of days apart in order to obtain blood samples for safety and research data at critical time points after each product administration. Note that these days are calendar days and not working business days. Therefore, the "Day of Study" is important to consider when scheduling or rescheduling a subject visit. All study visits are scheduled based on the date of the most recent product administration. Below is further explanation on scheduling.

Visit 02 (Day 0) = first product administration visit. Study Visits 02A through 05 must be scheduled based on the date of the first product administration.

Visit 05 = second product administration visit. Study Visits 05A through 09 must be scheduled based on the date of Visit 05. For example, if Visit 05 occurs +/-7 calendar days outside of the visit window, then Visits 03A through 09 must also be moved ahead +/-7 calendar days. If the second product administration does not occur, then schedule all follow-up visits based on the date of the first product administration.

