4.4.3 Dose-Limiting Toxicity

Dose-limiting toxicity is defined in this protocol as an AE that prevents a dose escalation of the study vaccine or prevents continuation of product administrations at a given dose level. If the study is paused as per criteria in [Section 4.4.1](#) and a decision is made to not resume the study vaccinations at the current dose, then the safety review will include a decision as to whether or not to continue accrual at a lower vaccine dose that was evaluated to be safe in order to achieve the target study accrual of 30 subjects.

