6.4.4 Immunogenicity Analysis

The statistical analysis for immunogenicity will employ the intent-to-treat principle, i.e., all data from randomized participants will be used. In the final analysis of immunogenicity, if there are cases of a subject receiving a schedule different from the assignment, then an as-treated analysis will be performed.

If assay data are qualitative (i.e., positive or negative) then analyses will be performed by tabulating the frequency of positive response for each assay at each time point that an assessment is performed. Binomial response rates will be presented with their corresponding exact 95% confidence interval estimates. Fisher's exact tests will be used to compare the two vaccine groups to each other. Missing responses will be assumed to be missing at random, i.e., conditional on the observed data the missingness is independent of the unobserved responses. Graphical descriptions of the longitudinal immune responses will also be given.

Some immunologic assays have underlying continuous or count-type readout that is often dichotomized into responder/nonresponder categories. For these assays, graphical and tabular summaries of the underlying distributions will be made. These summaries may be performed on transformed data (e.g., log transformation) to better satisfy assumptions of symmetry and homoscedasticity.

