6.4.6 Interim Analyses of Immunogenicity

An interim analysis of immunogenicity data may be performed when half of vaccinated participants reach the primary endpoint for immunogenicity evaluation at 4 weeks after the last product administration. Reports will be provided to the Protocol Chairs, and other key VRC investigators solely for the purpose of informing future trial-related decisions in a timely manner. Results will remain confidential and should in no way influence the conduct of the VRC 313 trial in terms of early termination or later safety or immunogenicity endpoint assessments.

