6.5 Randomization of Intervention Assignments

Randomizations will be done online using an electronic randomization system. The randomization code will be prepared by the Protocol Statistician and included in the randomization module for the trial. The randomization code will link to the intervention assignment. The electronic data system will assign each subject a randomization code after eligibility has been confirmed in the system.

At the beginning of the study, subjects will be randomized 1:1 to Groups 1 and 2. If the criteria for the first dose escalation are met and procedures for the interim safety review are completed, subjects can be randomized 1:1 to Groups 3 and 4. For practical purposes, accrual and randomization to Groups 1 and 2 should be completed as per study plan before accrual to Groups 3 and 4 begins.

If the criteria for the second dose escalation are met and procedures for the interim safety review are completed, subjects can be randomized 1:1 to Groups 5 and 6. For practical purposes, accrual and randomization to Groups 3 and 4 will be completed as per study plan before accrual to Groups 5 and 6 begins.

The subject and study clinicians will be informed on the subject's group assignment upon completing randomization in the electronic data collection system.

To decrease the potential for subject dropouts during the period between randomization and product administration will occur on Day 0 when eligibility is confirmed. If subjects accrued to a study group do not complete the number of vaccinations and follow-up duration specified, then additional subjects may be accrued in that group.

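### Does timing the main immunogenicity evaluation from the second vaccination in some sections and from the last administration in others leave the endpoint unsettled?

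*Combined protocol and SAP*

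**What the plan says.** Two sections tie the main immunogenicity time point to dose 2. Section 6.2.2 has "The primary time point for immunogenicity evaluation is 4 weeks after the second vaccination", and Section 1.6 has "The primary immunogenicity timepoint is 4 weeks after the second vaccination". Two others tie it to the final dose received. Both secondary objectives in Section 3.2 are set "at 4 weeks after the last product administration by virus-specific neutralization assays", and Section 6.4.6 refers to the "primary endpoint for immunogenicity evaluation at 4 weeks after the last product administration".

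The protocol provides for subjects who receive one dose. Section 4.5.1 lists reasons for withholding dose 2. Section 4.4.3 covers the case where "a decision is made to not resume the study vaccinations at the current dose". Section 4.2.5 says: "If the second product administration does not occur, then schedule all follow-up visits based on the date of the first product administration". Section 4.2.7 and Appendix III keep such subjects in follow-up to Week 36. Where subjects do not complete their vaccinations and follow-up, Section 6.5 adds: "then additional subjects may be accrued in that group".

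On analysis, Section 6.4.4 applies intent-to-treat to all randomized participants and tabulates response at each assessed time point. It adds that "if there are cases of a subject receiving a schedule different from the assignment, then an as-treated analysis will be performed". Section 6.4.5 includes every sample available at each time point.

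**The concern.** The plan appears to have two definitions of its main immunogenicity endpoint, with no rule for choosing between them when dose 2 is not given. A one-dose subject then has three possible treatments: the Day 28 result, no result, or the Day 84 result taken 12 weeks after a single injection.

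With five per group, that choice could move a reported rate noticeably, and in an open-label trial it would be made by people who may already have seen the data. If a whole dose level stopped before Week 8, one wording would give an endpoint for the group and the other would give none. The as-treated clause offers no obvious home for these subjects, because no group in Table 1 has a one-dose schedule. Section 6.5 does not say whether a replaced subject is still counted.

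**Working it through.** **Which visit each wording selects** (Appendix III: dose 1 on Day 0, dose 2 on Day 56, antibody samples at Visit 04 on Day 28 and Visit 07 on Day 84).

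| Subject | 4 weeks after second vaccination (1.6, 6.2.2) | 4 weeks after last administration (3.2, 6.4.6) |
|---|---|---|
| Both doses | 56 + 28 = Day 84, Visit 07 | 56 + 28 = Day 84, Visit 07 |
| Dose 1 only | none | 0 + 28 = Day 28, Visit 04 |

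For the one-dose subject, Visit 07 stays at Day 84 from dose 1, which is 84/7 = 12 weeks after the only injection.

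**The plan's own figures.** Section 6.3.2 reproduces at n = 5. With a true rate of 0.20, P(at least one response) = 1 − 0.8^5 = 0.672 and P(at least two) = 0.263. The exact 95% interval for 2/5 is 0.053 to 0.853. None of these depends on the time-point wording.

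**How often it could arise.** The plan gives no rate for missed second doses. As an assumption, take the phase 2 vaccine arm in Section 1.4.1, where 192 of 201 received both: p = (201 − 192)/201 = 9/201 = 0.0448, exact 95% interval 0.021 to 0.083.

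- Expected among 30: 30 × 0.0448 = 1.34.
- At least one among 30: 1 − (1 − p)^30 = 0.747, ranging from 0.471 to 0.926 over that interval.
- At least one in a given group of five: 1 − (1 − p)^5 = 0.205, ranging from 0.101 to 0.352.

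These are upper illustrations. The 9 missed dose 2 for any cause, and Section 1.4.1 does not say how many stayed in follow-up. Someone who left would have no Day 84 sample and perhaps no Day 28 sample. Section 4.5.1 also ends research sampling in pregnancy, which is itself a listed reason to withhold dose 2.

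**What one such subject does to a group of five.** Suppose all four two-dose subjects respond.

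| Handling of the fifth subject | Rate | Exact 95% interval |
|---|---|---|
| Left out | 4/4 = 100% | 39.8 to 100 |
| Counted, no response | 4/5 = 80% | 28.4 to 99.5 |
| Counted, response | 5/5 = 100% | 47.8 to 100 |

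The largest gap is 20 points, and it needs a non-response in the one-dose subject. With a replacement who responds, the corresponding results are 5/5 (47.8 to 100), 5/6 = 83% (35.9 to 99.6) and 6/6 (54.1 to 100), a gap of up to 17 points. The intervals overlap heavily.

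**What the plan already settles.** Intent-to-treat in Section 6.4.4 keeps a replaced subject in, because that subject was randomized. Section 6.4.5 then sets each visit's denominator as those with a sample. Section 6.4.4 tabulates each assessed time point, and Section 3.3 makes the other time points exploratory objectives. Where the samples exist, the Day 28 and Day 84 rates both appear under either wording. The open question is which of them carries the endpoint label for a one-dose subject.

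**As-treated clause.** It depends on receiving a different schedule. Section 6.3.3 uses schedule as a synonym for study group when introducing Table 4. On that reading the clause covers a subject given another group's product, and no one-dose group is needed. The text does not say whether a missed second dose also counts.

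**Missing-data wording.** Section 6.4.4 assumes missing at random and Section 6.4.5 missing completely at random. Tabulating the available samples gives the same numbers under both.

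**The case for a change.** The best argument for a change is that it would be cheap and would remove an analyst's choice in an open-label study. The choice can matter even to a test. With three responders among four two-dose subjects and a non-responding one-dose subject, Fisher's exact test (two-sided) against 0/5 gives p = 0.167 for 3/5 but p = 0.048 for 3/4. If a dose level stopped after all its first doses and before any second, up to five per group would have the endpoint under Section 3.2 and none under Section 6.2.2.

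Part of this stands. Both wordings are in current text, no sentence names the endpoint sample for a one-dose subject, and the as-treated clause can be read two ways.

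The inference to a needed amendment does not stand. Section 6.3.3 says the study is not powered for group comparison, and the largest power in Table 4 is 14%, so a p-value crossing 0.05 at five against four or five carries little weight. A stopped dose level would itself be a main finding, and its one-dose results would have to be described as such. The obvious repair also has a flaw. Fixing the label at four weeks after the second vaccination while counting every randomized subject in the Visit 07 row would put samples taken 12 weeks after one dose under a label that does not describe them.

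**Conclusion.** The difference in wording is real but clerical for a two-dose regimen: for every subject treated as planned, the last administration is the second vaccination and the visit is the same. For one-dose subjects it leaves a label undefined. It does not lose data or leave the visit denominators open.

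The effect is at most 20 points in one group's rate for one such subject, or 17 points with a replacement, always within very wide intervals. This is a secondary endpoint. No rule in the plan acts on the rate, and Section 6.4.6 bars interim immunogenicity results from influencing the trial's conduct. No stated figure is wrong, and no direction of bias is claimed.

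No change to the plan follows. A statistician preparing the tables would report Visit 07 by assigned group, footnote anyone who had one dose, and show those subjects' Day 28 and Day 84 results separately. This conclusion assumes that one-dose subjects are few. The 75% and 20% probabilities rest on the rate borrowed from another vaccine's trial and overstate how often competing samples would actually exist.

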6.2.3 Exploratory Endpoints: Immunogenicity

Exploratory immunogenicity endpoints are measured by virus-specific neutralization assays, ELISA, and other research tests as described in Section 1.6

6.3 Sample Size and Accrual

Recruitment will target 30 healthy adult participants divided equally among 6 groups.

6.3.1 Power Calculations for Safety

The goal of the safety evaluation for this study is to identify safety concerns associated with product administration of the investigational vaccine. Primary sample size calculations for safety are expressed in terms of the ability to detect serious adverse experiences.

The ability of the study to identify SAEs will be expressed in terms of the probability of observing a certain number of SAEs. Useful values are the minimum true rate such that the probability of observing at least one event is at least 90%, and the maximum true rate such that the probability of not observing any event is at least 90%. Within each group (n=5), there is over 90% chance to observe at least 1 SAE if the true rate is at least 0.37 and over 90% chance to observe no SAE if the true rate is no more than 0.02.

Probabilities of observing 0 or more than 1 SAE within each group are presented in Table 2 for a range of possible true event rates. These calculations provide a more complete picture of the sensitivity of this study design to identify potential safety problems with the vaccine.

Table 3 gives the upper and lower bounds for 95% exact binomial confidence intervals of the true SAE rate at all possible numbers of events within each group (n=5). If none of the 5 vaccines experience serious adverse events, the 95% exact 2-sided upper confidence bound for the SAE rate is 0.522.

Table 2: Probability of Events for Different Safety and Immunogenicity Scenarios within a Group (n=5)

True Event rate	Pr (observing 0 event)	Pr (observing more than 1 event)
0.005	0.975	0
0.01	0.951	0.001
0.02	0.904	0.004
0.035	0.837	0.011
0.05	0.774	0.023
0.1	0.59	0.081
0.15	0.444	0.165
0.2	0.328	0.263
0.3	0.168	0.472

Table 3: 95% Confidence Intervals for the True Rate At All Possible Observed Rates within a Group (n=5)

Observed Rate	95% Confidence Interval	
	Lower Bound	Upper Bound
0/5	0	0.522
1/5	0.005	0.716
2/5	0.053	0.853
3/5	0.147	0.947
4/5	0.284	0.995
5/5	0.478	1

6.3.2 Sample Size Calculations for Immunogenicity

Table 2 gives the probabilities of observing 0 or at least 2 responses over a range of underlying response rates. For example, if the true response rate at a particular time point is 0.20, then there is a probability of 0.672 to observe at least one response and a probability of 0.263 to observe at least 2 responses among the 5 vaccinees in a group.

Table 3 is applicable to the immunogenic response rates, and gives the exact 95% confidence interval of the true response rate over possible number of responses out of the 5 subjects. For example, if we observe 2 responses among the 5 vaccinees, the 95% exact binomial confidence interval of the true response rate will range from 0.053 to 0.853.

